PAH is a progressive disease ultimately leading to cardiac failure and death if untreated. Preclinical data suggest that LTP001 may reduce pulmonary artery pressure and thus may control or reverse disease progression. However, the clinical data with LTP001 is still limited. It has been used in a Phase I study in healthy participants. It is used in the parent study, CLTP001A12201, for this extension study as well as in clinical investigations in other indications, such as lung fibrosis. Thus, when this extension study starts, whilst there will be a safety record in healthy and PAH participants, efficacy may not yet be proven in PAH participants.

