2.1.1 General definitions

Investigational treatment will be LTP001.

Date of first administration of study treatment (Day 1) will be defined as the date of the first actual administration of LTP001.

Date of last administration of study treatment will be defined as the date of the last actual administration of LTP001.

Two *Baselines* will be defined as the following:

Baseline of the Parent study: the Day 1 assessment of study LTP001A12201. If this datum is not available, the last pre-dosing assessment will be considered.

Baseline of the Extension study: Week 25 visit from LTP001A12201. If this datum is not available, the last pre-dosing assessment for this study (LTP001A12201E1) will be considered. *Study day* will be defined as the number of days since the date of first dose of study treatment (LTP001 or placebo). The date of first dose of study treatment will be defined as *Day 1* and the day prior to first dose of will be defined as *Day -1*. Therefore, for a particular date, study day will be calculated as follows:

for dates on or after the date of first dose of study treatment,

Study day = Assessment date – Date of first dose administration + 1

The on-treatment period lasts from the date of first administration of study treatment to the End of Study (EOS) visit or the date of last randomized dose if EOS visit is not available. The EOS visit is a follow-up visit that is approximately 30 days after the date of the last actual administration of investigational treatment. For participants who will be enrolled into the open label extension (OLE) study, their EOS visits will be skipped.

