2.6.1.1 Efficacy and/or pharmacodynamic endpoints(s)

All analyses will be conducted using PD analysis set.

Change from baseline for efficacy endpoints will be descriptively summarized by visit/time for treatment group assigned in the parent study, and overall. Two baseline measurements will be generated as per [Section 2.1.1](#). Graphs (e.g., spaghetti plot) will be provided to show individual time courses of parameters for the extension study together with the parent study.

Additionally, two changes from baseline values for efficacy endpoints will be descriptively summarized by visit/time for treatment group assigned in the parent study, and overall with the following comparisons:

- a) Short-term (change from baseline of extension study) vs. long-term (change from baseline of the parent study) treatment effect (For both treatment and placebo groups assigned in the parent study).
- b) the treatment group difference (assigned in the parent study) within each change from baseline value.

6MWD

This measures how many meters a person can walk in 6 minutes. It includes total distance walked (6MWD), the number and duration of any stops in 6 minutes. Test performed at baseline and at visits on Day 176 and 358 will be used for analysis.

Descriptive statistics (N, mean, SD, CV% mean, geometric mean, CV% geometric mean, median, min, and max) summarizing 6MWD parameters and their changes from baseline will be summarized by visit/time for treatment group assigned in the parent study and overall.

Panels of individual spaghetti plots over time/visit for treatment group assigned in the parent study and overall for each 6MWD parameter will be provided.

All 6MWD parameters will be listed by participant, and visit and if ranges are available, abnormalities will be flagged.

RHC

The RHC is performed to assess several hemodynamic parameters when the patient is in a stable hemodynamic rest state (as demonstrated by three consecutive cardiac output measurements with 10% of each other). The measurement is taken at baseline and at visit on Day 176. The assessed hemodynamic parameters include:

- PVR
- right atrial (RA) pressure
- mean pulmonary artery pressure (mPAP)
- pulmonary capillary wedge pressure (PCWP)
- systolic and diastolic blood pressure (RV pressures)
- heart rate (HR)
- cardiac output (CO)
- systemic vascular resistance (SVR)
- mixed venous blood gas measurement

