Descriptive statistics (N, mean, SD, CV% mean, geometric mean, CV% geometric mean, median, min, and max) summarizing RHC parameters and their changes from baseline will be summarized by visit/time for treatment group assigned in the parent study and overall.

Panels of individual spaghetti plots over time/visit for treatment group assigned in the parent study and overall for each RHC parameter will be provided.

All RHC parameters will be listed by participant, and visit and if ranges are available, abnormalities will be flagged.

Echocardiography/RVF

The echocardiography is performed to assess the impact of study drug on right heart structure and function. All echocardiography images will be centrally read by an imaging vendor. The measurement is taken at baseline and at visit on Day 176 and 358.

The assessed echocardiography parameters include:

- Tricuspid annular plane systolic excursion (TAPSE)
- Tricuspid annular systolic velocity (TASV)
- Peak velocity of excursion (RV S')

- Fractional area change (FAC)

Descriptive statistics (N, mean, SD, CV% mean, geometric mean, CV% geometric mean, median, min, and max) summarizing echocardiography parameters and their changes from baseline will be summarized by visit/time for treatment group assigned in the parent study and overall.

Panels of individual spaghetti plots over time/visit for treatment group assigned in the parent study and overall for each echocardiography parameter will be provided.

All echocardiography parameters will be listed by participant, and visit and if ranges are available, abnormalities will be flagged.

Time to clinical worsening (TTCW)

TTCW will be defined as time to any of the following events

- Death
- Hospital stay (≥ 24 h) due to worsening of PAH. Worsening of PAH is defined by the following right heart failure related signs and symptoms: syncope or near syncope, cyanosis, increase of breathlessness, clinically relevant deterioration of exercise capacity, decrease of oxygen saturation, increased peripheral edema, hepatomegaly, and ascites
- Worsening of PAH resulting in need for lung transplantation or balloon atrial septostomy
- Initiation of parenteral prostanoid therapy, chronic oxygen therapy, or any other PAH-specific therapies or need for increase of diuretics for more than 4 weeks due to worsening of PAH
- Disease progression (switch in modified New York Heart Association/WHO FC by at least one grade)

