- Significant drop in 6MWD (15% from baseline or more) due to PAH-worsening

Time to clinical worsening will be analyzed using survival models (i.e., Kaplan-Meier, cox regression) if adequate number of events occur during the study to characterize the survival curve. Participants without the event will be considered as censored at the end of the time at risk. The hazard ratio between the treatment group assigned in the parent study and the corresponding 80% confidence intervals will be computed using the appropriate method. If there is no adequate number of events, the number (and percentage) of participants with clinical worsening will be summarized by treatment group assigned in the parent study and overall.

NT-proBNP

Descriptive statistics (N, mean, SD, CV% mean, geometric mean, CV% geometric mean, median, min, and max) summarizing N-terminal fragment of the prohormone B-type natriuretic peptide , NT-proBNP (visits on Day 29, 85, 176, 267 and 358) and its changes from baseline will be summarized by visit/time for treatment group assigned in the parent study and overall.

Spaghetti plot over time/visit will be provided. And the endpoint will be listed by participant, and visit and if ranges are available, abnormalities will be flagged.

Change from baseline for efficacy endpoints will be descriptively summarized by visit/time for treatment group assigned in the parent study, and overall. The baseline measurement for the extension will be the baseline measurement taken during the parent study CLTP001A12201. Graphs (e.g., spaghetti plot) will be provided to show individual time courses of parameters for the extension study together with the parent study.

Additionally, changes from baseline for efficacy endpoints will be descriptively summarized by visit/time for treatment group assigned in the parent study, and overall using a different baseline strategy: participants receiving LTP001 in the parent study will use the baseline of parent study as the baseline; participants switching from placebo in parent study to LTP001 in extension study will use the baseline of extension study as the baseline.

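### SAP 2.6.1.1 lists geometric mean and geometric CV% for changes from baseline, where both are undefined as soon as one change is zero or negative

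*SAP*

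**What the plan says.** SAP 2.6.1.1 gives one list of nine statistics and applies it to values and to changes alike. For the walk test the text is "Descriptive statistics (N, mean, SD, CV% mean, geometric mean, CV% geometric mean, median, min, and max) summarizing 6MWD parameters and their changes from baseline". The same list precedes "summarizing RHC parameters and their changes from baseline will be summarized by visit/time" and "summarizing echocardiography parameters and their changes from baseline will be summarized by visit/time", and for the biomarker it covers "NT-proBNP (visits on Day 29, 85, 176, 267 and 358) and its changes from baseline will be summarized".

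The walk-test parameters are wider than the distance: "It includes total distance walked (6MWD), the number and duration of any stops in 6 minutes".

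SAP 2.1 and 2.1.1 call for change against two baselines and define those baselines. They do not define change as a ratio to baseline or on the log scale. No section of the SAP gives a rule for zero or negative values. The laboratory summaries in SAP 2.5.1 also cover results and changes, but their list (N, mean, SD, minimum, median, maximum) has no geometric statistics.

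**The concern.** A geometric mean and a geometric CV% are functions of log values, so every value must be positive. A change from baseline is a difference and can take either sign. The documents themselves foresee falls:

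- One component of clinical worsening is "Significant drop in 6MWD (15% from baseline or more) due to PAH-worsening".
- Protocol 2.3 states: "Preclinical data suggest that LTP001 may reduce pulmonary artery pressure and thus may control or reverse disease progression". For mean pulmonary artery pressure the hoped-for change is therefore negative.
- SAP 2.1.1 sets "Baseline of the Extension study: Week 25 visit from LTP001A12201". For participants who took LTP001 in the parent study, this is an on-treatment value. The documents give no reason to expect every later change from it to go one way.

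Followed literally, the rule leads to one of two outcomes. Either the cell is empty, or non-positive changes fall out when logs are taken. The second is worse: the table would show a positive figure based only on participants whose values rose, in a row that appears to describe everyone.

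**Working it through.** The plan gives no figure to reproduce: the sample size sections of both documents are marked not applicable. The definitions settle the point, and the probabilities below only show how often it would bite.

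**Definitions.** Geometric mean = exp(mean of ln x). Geometric CV% = 100·sqrt(exp(s²) − 1), where s is the SD of ln x. Both need every x > 0.

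**Small invented examples (changes in metres).**
- {−30, 0, 15, 25, 40}: both undefined. The arithmetic mean is +10. Dropping the two non-positive values leaves {15, 25, 40}, with geometric mean (15·25·40)^(1/3) = 24.7.
- {0, 15, 25, 40}: geometric CV% undefined. The geometric mean is undefined in log form and 0 in product-root form.
- {−30, −10, 15, 25}: both undefined in log form. The product-root form returns 18.3, although the arithmetic mean is 0.

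**How often the statistic would exist.** Inputs: Protocol section 5 expects about 40 participants to complete the parent study and meet the entry criteria. Entry is voluntary, summaries are by parent-study group as well as overall, and SAP 2.6.4 leaves missing values unimputed unless stated. I therefore take n = 10 to 40 as an assumed range. The documents give no SD, group size or expected change, so the mean change in SD units (m) is also assumed. For independent normal changes, P(all n changes > 0) = Φ(m)^n.

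| m | Φ(m) | n=10 | n=20 | n=40 |
|---|---|---|---|---|
| 0 | 0.500 | 0.1% | <0.001% | <0.001% |
| +0.5 | 0.691 | 2.5% | 0.06% | <0.001% |
| +1 | 0.841 | 18% | 3.2% | 0.1% |
| +2 | 0.977 | 79% | 63% | 40% |

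At m = −0.5, Φ(m) = 0.309 and the chance is below 0.001% even at n=10. An even chance needs m = Φ⁻¹(0.5^(1/n)), which is +1.50, +1.82 and +2.12 SD for n = 10, 20 and 40.

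With heavier tails (t with 5 df scaled to SD 1) and m = +1, the chance is 6.7% at n=20 and 0.4% at n=40. These exceed the normal figures but remain small.

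**If non-positive changes are dropped.** Assume normal changes with mean −5 and SD 10. Then 31% are positive (Φ(−0.5) = 0.309), and the geometric mean of that part of the distribution is about +4.1. The true mean change is −5.

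**Raw stops.** If a share p of participants do not stop, the chance that no count is zero is (1 − p)^n. For assumed p = 5%, 10% and 50% this is 60%, 35% and 0.1% at n=10; 36%, 12% and <0.001% at n=20; and 13%, 1.5% and <0.001% at n=40. The same holds for duration only if non-stoppers are coded 0 rather than missing, which the documents do not state.

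**The case against.** The best defence is that the matter is small. The analyses are descriptive, the list is repeated for four endpoint groups and looks like template text, and a programmer would probably print a not-calculable cell. The SAP introduction also refers to wider reporting and analysis documents; table shells are not among the documents available here and could hold a where-calculable rule. All of this limits the weight of the point. It does not change the SAP wording, which names changes explicitly in all four groups.

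A reader might infer more than the text supports:

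- *That the two statistics can never be produced for change.* They can whenever all changes in a cell are positive. At a mean of +2 SD that happens in 40% to 79% of cases for n between 40 and 10.
- *That CV% mean is invalid too.* Negative individual changes do not break it. It becomes unstable only when the mean change is near zero, and negative when the mean is negative.
- *That both stop variables must fail as raw values.* The number of stops does so if anyone does not stop; duration depends on coding.
- *That the efficacy summaries as a whole are compromised.* N, mean, SD, median, minimum, maximum, plots and listings are all unaffected.

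**Conclusion.** The point holds in a conditional form. For absolute changes from baseline, the log-based geometric mean and geometric CV% are undefined whenever at least one change is zero or negative. The documents foresee such changes, and the SAP neither defines change on another scale nor gives a rule for these values. This is a listed statistic that does not suit its variable, rather than a missing detail.

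With 10 to 40 participants per cell, the statistics would usually not exist unless the mean change were about +1.5 to +2.1 SD or more. That sizing rests on assumed n, independence, normality and an assumed mean change. The definitional conclusion rests on none of these.

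The severity is low. The affected cells are in secondary descriptive tables, the primary safety summaries use other lists, and no decision rule in either document depends on them.

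**What to change.** In SAP 2.6.1.1, split the sentence for each of the four endpoint groups:

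1. For absolute changes from baseline, remove geometric mean and CV% geometric mean. The laboratory list in SAP 2.5.1 is a ready model. Removing CV% mean as well is optional.
2. For raw values, keep the geometric statistics only for strictly positive parameters, and not for number or duration of stops.
3. If a log-scale summary of change is wanted (for example NT-proBNP or PVR), report the geometric mean ratio to baseline, exp(mean of log(visit/baseline)), with geometric CV% = 100·sqrt(exp(s²) − 1), where s is the SD of the log ratios. For example, invented baselines of 400, 350, 380, 420 and 300 m with changes of −30, 0, +15, +25 and +40 m give a ratio of 1.029 and a geometric CV of 7.5%, whereas on the raw changes neither exists.

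The cost is SAP wording and table-shell edits, best made before database lock. No new data are needed. Protocol 9.4.1 asks only for descriptive summaries and names no geometric statistic, so its text need not change.

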This is a non-randomized, open-label extension study, over 52 weeks, with LTP001 without a control treatment arm. Participants will be presented the opportunity to consider the extension study at the End of Treatment (EOT) visit of the parent study CLTP001A12201. At the EOT visit of the parent study, the investigator will determine the eligibility for the extension study (i.e. that none of the treatment discontinuation criteria were met and that the assessments at the EOT of the parent study were completed according to the parent protocol). Participants who are eligible and want to participate in the extension study will need sign an informed consent to receive the extension study treatment. As not all assessment results will be available (e.g. lab assessments) at the same visit date, the investigator will re-assess/reconfirm the eligibility as soon as the outstanding results are received. Patients can directly transition into treatment in this extension study without un-blinding the previous treatment in the parent study. The safety and efficacy of LTP001 will be checked at the following visits: Weeks 5, 13, 26, 39, and 52, as specified in the schedule of activities. Safety and tolerability assessments will take place at each visit. 6MWT and echocardiography will be assessed at Weeks 26 and 52. RHC will be assessed at Week 26. PAH-SYMPACT and emPHasis-10 will be collected for 7 day intervals with the seventh day of collection occurring within the allotted visit window for all visits. Participants will have safety follow-up phone calls at Weeks 9 and 17, and may be invited for unscheduled assessments at the site if deemed necessary. Following the end of the treatment period, participants will have one safety follow-up phone call approximately 30 days after the end of treatment visit at Week 56.

The safety and efficacy profile of LTP001 that is observed in this extension study as well as the parent study, CLTP001A12201, will determine continuation of the extension study.

Brief Summary:

The purpose of this study is to measure the long-term safety and efficacy profile of LTP001 in participants with pulmonary arterial hypertension (PAH). The study offers participants who had completed the CLTP001A12201 double-blind parent study in PAH an opportunity to receive LTP001 (whether they were on LTP001 or not). Unblinding of the treatment received in CLTP001A12201 is not planned.

- The study duration will be up to 54 weeks.

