1.2 Schema**Figure 1-1 Study Schema****1.3 Assessment Schedule**

The Assessment Schedule lists all of the assessments when they are performed. All data obtained from these assessments must be supported in the participant's source documentation. The "X" in the table denotes the assessments to be recorded in the clinical database or received electronically from a vendor. The "S" in the table denotes the assessments that are only in the participant's source documentation and do not need to be recorded in the clinical database.

Participants should be seen for all visits/assessments as outlined in the Assessment Schedule or as close to the designated day/time as possible. Missed or rescheduled visits should not lead to automatic discontinuation.

Participants who discontinue from study treatment are to complete the end of treatment visit as soon as possible, and attend the follow-up visits as indicated in the Assessment Schedule.

Participants who discontinue from study should be scheduled for a final evaluation visit if they agree, as soon as possible, at which time all of the assessments listed for the final visit will be performed. At this final visit, all dispensed investigational product should be reconciled, and the adverse events and concomitant medications not previously reported must be recorded on the CRF.

PRO measures must be completed before any assessments are performed at any given visit.

As per [Section 4.5](#), during a public health emergency as declared by local or regional authorities (i.e. pandemic, epidemic or natural disaster that limits or prevents on-site study visits), alternative methods of providing continuing care may be implemented by the Investigator as the situation dictates. If allowable by a local health authority, national and local regulations and depending on operational capabilities, phone calls, virtual contacts (e.g. tele consultation) or visits by site staff/ off-site healthcare professional(s) staff to the participant's home, can replace certain protocol assessments, for the duration of the disruption until it is safe for the participant to visit the site again. If the Investigator delegates tasks to an off-site healthcare professional, the Investigator must ensure the individual(s) is/are qualified and appropriately trained to perform assigned duties. The Investigator must oversee their conduct and remain responsible for the evaluation of the data collected.

Table 1-2 Assessment Schedule

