Period	Baseline		Extension Treatment Up To Month 12							
Visit Name	Transition Period		Treatment						EOT	Post Study Safety Contact
Visit Numbers ¹	1 ²	100 ²	110		120		130	140	150	
Days	-14 to -1	1	29 ±7	57 ±10	85 ±10	113 ±10	176 ±10	267 ±10	358 ±10	Last treatment +30 -0 +7
Weeks	-2 to -1	1	5 ±1	9 ±2	13 ±2	17 ±2	26 ±2	39 ±2	52 ±2	57 -0 +1
Informed consent ^{3,4}	X									
Inclusion / Exclusion criteria	X									
Physical Examination			S	S ⁸	S	S ⁸	S	S	S	
Body Weight			X	X ⁸	X	X ⁸	X	X	X	
Body Temperature			X	X ⁸	X	X ⁸	X	X	X	
Blood Pressure and Pulse Rate			X	X ⁸	X	X ⁸	X	X	X	
Electrocardiogram (ECG)			X	X ⁸	X	X ⁸	X	X	X	
Dose administration ⁵	X	X	X ⁸	X	X ⁸	X	X	X	X	
Drug dispensation	X	X		X			X	X		
Collect study medication/perform drug accountability ⁵			X	X ⁸	X	X ⁸	X	X	X	
Urinalysis			X	X ⁸	X	X ⁸	X	X	X	
Pregnancy and assessments of fertility			S	S ⁸	S	S ⁸	S	S	S	
Hematology			X	X ⁸	X	X ⁸	X	X	X	
Clinical Chemistry			X	X ⁸	X	X ⁸	X	X	X	

Period	Baseline		Extension Treatment Up To Month 12								
Visit Name	Transition Period		Treatment						EOT	Post Study Safety Contact	
Visit Numbers ¹	1 ²	100 ²	110		120		130	140	150		
Days	-14 to -1	1	29 ±7	57 ±10	85 ±10	113 ±10	176 ±10	267 ±10	358 ±10	Last treatment +30 -0 +7	
Weeks	-2 to -1	1	5 ±1	9 ±2	13 ±2	17 ±2	26 ±2	39 ±2	52 ±2	57 -0 +1	
Coagulation Panel			X	X ⁸	X	X ⁸	X	X	X		
NT-proBNP				X		X		X	X		
emPHasis-10 and PAH-SYMPACT ⁶			X ⁷		X ⁷		X ⁷	X ⁷	X ⁷		
Right Heart Catheterization ⁴							X				
6-Minute Walk Test ⁴							X		X		
Echocardiogram ⁴							X		X		
Concomitant Medications/Adverse Events								X			
Study completion information									X		

Period	Baseline		Extension Treatment Up To Month 12							
Visit Name	Transition Period		Treatment					EOT	Post Study Safety Contact	
Visit Numbers ¹	1 ²	100 ²	110		120		130	140	150	
Days	-14 to -1	1	29 ±7	57 ±10	85 ±10	113 ±10	176 ±10	267 ±10	358 ±10	Last treatment +30 -0 +7
Weeks	-2 to -1	1	5 ±1	9 ±2	13 ±2	17 ±2	26 ±2	39 ±2	52 ±2	57 -0 +1
Safety Follow up Call			S		S					S

^X Assessment to be recorded in the clinical database or received electronically from a vendor

^S Assessment to be recorded in the source documentation only

¹ Visit structure given for internal programming purpose only

² Baseline and Day 1 can be on the same day or within a 14-day transition period

³ CCI

⁴ Assessment must be performed onsite. All other assessments may be performed at an off-site location.

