2.3 Benefit/Risk assessment

Potential risks are based on the mechanism of action, the nonclinical toxicology data, and the safety data from the FIH study.

LTP001 is the first SMURF1 inhibitor to be developed. Based on current understanding of SMURF1 biology, there are no concerns directly related to this mechanism of action; and, because LTP001 is first-in-class, there are no previously identified clinical safety risks (i.e., no known class effects).

Preclinical data

CCI

CCI

Clinical data

Single doses of LTP001 CCI mg, CCI mg, CCI mg, CCI mg, CCI mg and CCI mg were well tolerated and did not show safety signals for LTP001 in the first in human study.

Multiple doses of LTP001 CCI mg, CCI mg, CCI mg, CCI mg and CCI mg once daily and CCI mg bid were well tolerated. CCI

CCI , clinical laboratory assessments, ECGs, and vital signs did not show significant abnormalities. CCI

The risk to participants in this trial will be minimized by adherence to the eligibility criteria, close clinical monitoring, regular safety data reviews, and pre-specified rules for automatically stopping the study should unanticipated safety issues suddenly arise.

No reproductive toxicology studies have been performed for LTP001. Women of child-bearing potential will be only enrolled if they use highly effective contraception methods.

Additional details about potential risks of LTP001 can be found in the Investigator's Brochure.

Procedural risks

Cardiac catheterization is a safe procedure when performed by an experienced medical team. However, there may be some possible risks such as bleeding, infection, and blood clots. A heart attack or a stroke can happen in very rare situations. Right heart catheterization (RHC) is regularly employed to monitor the course of PAH. RHC may be performed without radiation but for optimal placement of the catheter, the investigator can employ x-ray to double-check the positioning of the catheter when measurements are made. RHC does not employ contrast media. RHC is required to calculate PVR. PVR was the primary efficacy assessment of the

parent study, CLTP001A12201, and is performed at Week 26 in the current study, which allows the assessment of the 1-year effect of LTP001 of those participants who received LTP001 already in the parent study, and the 6-month effect on PVR of those who received placebo in the parent study. This data is considered very important to assess the long-term effect of LTP001 on PVR in patients with PAH.

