The safety and efficacy of LTP001 will be checked at the following visits: Weeks 5, 13, 26, 39 and 52, as specified in the Assessment Schedule. Safety and tolerability assessments will take place at each visit. RHC will be performed at week 26, 6MWT and echocardiography will be assessed at Weeks 26 and 52. PAH-SYMPACT and emPHasis-10 will be collected for 7 days intervals with the seventh day of collection occurring within the allotted visit window for all Treatment visits (Weeks 5, 13, 26, 39 and 52). Participants will have safety follow-up phone calls at Weeks 9 and 17, and may be invited for safety assessment at site if deemed necessary. The PI may exercise their discretion in which safety assessments are required at these optional safety follow-up visits. Following the end of treatment period, participants will have one safety follow-up phone call approximately 30 days after the end of treatment visit at Week 52. The duration of the extension study is currently restricted to 52 weeks, but the study may be prolonged (via an amendment to the protocol) if the LTP001 development program in PAH continues and the benefit/risk assessment remains favorable for the patient population studied. The safety and efficacy profile of LTP001 that is observed in this extension study as well as the parent study, CLTP001A12201, will determine continuation of the extension study.

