7.1 Discontinuation of study treatment

The investigator must also contact the IRT to register the participant's discontinuation from study treatment.

Discontinuation of study treatment for a participant occurs when study treatment is permanently stopped for any reason (prior to the planned completion of study drug administration, if any) and can be initiated by either the participant or the investigator.

The investigator must discontinue study treatment for a given participant if he/she believes that continuation would negatively impact the participant's well-being.

Discontinuation from study treatment is required under the following circumstances:

- Participant decision
- Pregnancy (if the participant decided to terminate the pregnancy, treatment with LTP001 may be resumed after the abortion procedure if desired by the participant and agreed by the investigator and the Novartis medical monitor).
- Any situation in which continued study participation might result in a safety risk to the participant
- Development of heart failure symptoms consistent with pulmonary hypertension WHO Functional Class IV (symptoms at rest; severe symptoms at exercise)
- If organ transplantation becomes necessary during the study treatment
- Atrial septostomy required due to deterioration of PAH
- Deterioration of PAH suggesting ineffectiveness of LTP001 as per the judgement of the investigator
- Adverse event that is graded severe or serious by the investigator and considered study drug related. If the investigator believes it is beneficial for the participant to stay on study drug (e. g. signs of PAH-improvement and adverse event appears well manageable) and the participant wishes to stay on study drug the investigator shall contact the Novartis medical monitor for further discussion.
- If a liver or renal event occurs, follow guidelines outlined in [Section 10.5](#) (Appendix 5) and [Section 10.6](#) (Appendix 6) regarding discontinuation of study treatment.

If discontinuation from study treatment occurs due to participant's decision, the investigator should make a reasonable effort to understand the primary reason for the participant's discontinuation from study treatment and record this information. In those instances where study drug discontinuation criteria were waived as per the exceptions defined above the decision made as well as the rationale for it needs to be documented in writing in the Trial Master File.

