2.6.4 Handling of missing values not related to intercurrent event

See each endpoint in [Section 2.6.1](#). If not specified, missing data will not be imputed.

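### Week 26 PVR is an observed-case summary with no RHC at end of treatment, so it is likely to lose participants who die or stop LTP001 for PAH worsening, and no planned output ties a missing RHC to its reason

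*SAP*

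**What the plan says.** **Timing.** For RHC, SAP 2.6.1.1 states "The measurement is taken at baseline and at visit on Day 176". Protocol 4.1 agrees: "RHC will be performed at week 26, 6MWT and echocardiography will be assessed at Weeks 26 and 52". In the Assessment Schedule (Protocol 1.3) the row "Right Heart Catheterization" has one mark, at Week 26, and none at end of treatment (EOT). The 6MWT and echocardiogram rows are marked at both. Protocol Table 3-1 and SAP Table 1-1 define the RHC endpoint as the change from baseline at Week 26.

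**Stopping early.** Protocol 7.1 requires LTP001 to be stopped for several PAH-related reasons. These include WHO Functional Class IV symptoms, transplantation, atrial septostomy and "Deterioration of PAH suggesting ineffectiveness of LTP001 as per the judgement of the investigator". Protocol 1.3 then says "Participants who discontinue from study treatment are to complete the end of treatment visit as soon as possible", with follow-up visits after that. Section 7.1 sets concomitant treatments and adverse events as the minimum to collect in abbreviated visits. The definition of treatment discontinuation in Protocol 10.2.2 is wider: the participant agrees to the other assessments that the protocol requires.

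**Analysis.** For secondary endpoints the SAP marks intercurrent events (2.6.3) and supplementary analyses (2.6.6) as not applicable. Section 2.6.4 says "If not specified, missing data will not be imputed", and nothing is specified for RHC. Section 2.6.5 discusses missing data for the 6MWT only.

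**Importance.** Of the Week 26 RHC, Protocol 2.3 says "This data is considered very important to assess the long-term effect of LTP001 on PVR in patients with PAH".

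**The concern.** Of the three main functional and hemodynamic measurements, RHC is the only one that cannot be picked up at an early EOT visit. A participant whose PAH worsens enough to stop LTP001 in month 3 has an EOT walk test and echocardiogram but, on the schedule, no PVR. That participant remains in the PD analysis set (SAP 2.2) and contributes nothing to the PVR table.

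Loss for this reason is informative about PVR, and its direction is predictable. Those who did badly go missing, so the remaining mean change looks better. The SAP also compares parent-study arms within each change from baseline, and unequal loss between arms would distort that comparison. The study's stated purpose is to help decide whether LTP001 merits further development in PAH, and the protocol singles out this measurement as important to that question.

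**Working it through.** **Step 1: follow an early stopper through the plan.**
- Before Week 26: LTP001 is stopped under Protocol 7.1, and EOT follows as soon as possible. EOT has no RHC.
- After EOT: the only scheduled contact is the safety call.
- At analysis: no imputation, no RHC sensitivity analysis, and therefore no value.

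There are two ways to have a Week 26 RHC despite deterioration. Protocol 2.3, 4.3.1 and 7.1 allow some participants to stay on LTP001 after discussion with the sponsor. The Protocol 10.2.2 definition leaves room for an RHC off drug. The documents do not say whether an off-drug value would enter the summary.

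**Step 2: see what the planned outputs reveal.**
- The RHC table (SAP 2.6.1.1) gives N by arm, which shows how many are missing but not why.
- Disposition (SAP 2.3.1) counts discontinuation from the study by reason. It does not count discontinuation from treatment or loss before the RHC.
- Deaths and AEs leading to discontinuation are summarized (SAP 2.5.1), and clinical worsening is analysed as TTCW. Neither is joined to missing PVR.

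**Step 3: illustrate the size.** There is no plan figure to reproduce. Sample size is marked not applicable, and no discontinuation rate, SD or effect is given. The one input from the documents is N of about 40 (Protocol 5). The rest are assumptions: fraction missing p of 10% or 20%; those missing d SD worse on average, with d = 0.5, 1 or 1.5; roughly normal changes among those measured.

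*Mean.* If those measured have mean m, the full-group mean is (1−p)m + p(m+d) = m + pd. The observed mean is too favourable by p × d. Its standard error is 1/√n in SD units.

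| p | Missing / measured | p × d for d = 0.5, 1, 1.5 | SE | Ratio to SE at d = 1 |
|---|---|---|---|---|
| 10% | 4 / 36 | 0.05, 0.10, 0.15 SD | 1/√36 = 0.167 | 0.6 |
| 20% | 8 / 32 | 0.10, 0.20, 0.30 SD | 1/√32 = 0.177 | 1.1 |

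*Median with worst ranks.* If a fraction q of those ranked is placed worst, the overall median falls at the 0.5/(1−q) quantile of the measured values. The shift is z(0.5/(1−q)). Suppose half of those missing are deaths or PAH-worsening stops and the rest are left out:
- 10% missing: 2 worst among 38 ranked. q = 0.053, 0.5/0.947 = 0.528, shift 0.07 SD.
- 20% missing: 4 worst among 36 ranked. q = 0.111, 0.5/0.889 = 0.5625, shift 0.16 SD.

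The bounds are no shift if none are PAH-related, and z(0.5/0.9) = 0.14 SD or z(0.5/0.8) = 0.32 SD if all are.

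**The case against.** The strongest reply is that the plan does have a rule. SAP 2.6.4 leaves missing data unimputed, so RHC is an observed-case summary, which is a legitimate choice in a descriptive extension. Safety is the primary objective, there is no concurrent control, PVR was the primary efficacy assessment of the parent study, and no RHC test can change. The reply adds that N, participant listings, spaghetti plots, disposition, deaths and TTCW already let a reader see most of the loss.

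Much of this stands. A reader might infer that the SAP is silent on missing RHC, that the result covers only participants still on drug with all treatment failures removed, or that the loss cannot be seen at all. The documents do not support any of these:
- The default in 2.6.4 is a rule, although it does not address why values are missing.
- Some deteriorating participants may stay on LTP001, and an off-drug Week 26 RHC is conceivable.
- The list in Protocol 7.1 is the minimum to be collected, not the only data allowed.
- The planned outputs give a partial view.

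The size is also conditional. Participants who leave because of an unrelated AE or by their own decision need not have worse PVR, so ranking every leaver worst gives an upper bound.

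What the reply leaves open is the link. No planned table says, by arm, how many Week 26 RHC values are missing because the participant died or got worse.

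**Conclusion.** The point holds as a moderate one about interpretation. With one RHC in the extension, none at EOT and no imputation, the Week 26 PVR summary will generally omit participants who die or stop LTP001 for PAH worsening before Week 26. It is therefore likely to be too favourable. The direction follows from the protocol's own stopping reasons; the amount does not follow from anything in the documents.

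With 10-20% missing and all of them 1 SD worse, the mean is off by 0.10-0.20 SD, about 0.6 to 1.1 standard errors. With half of those missing ranked worst, the overall median moves by about 0.07-0.16 SD. The loss fraction, the 1 SD deficit and the one-half split are all assumptions.

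Participants who stop after their Week 26 RHC are unaffected. The change should be made before database lock, but the safety conclusions do not depend on it.

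**What to change.** In the RHC part of SAP 2.6.1.1, with no extra catheterization:

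1. Tabulate, by parent-study arm and overall, the number in the PD analysis set without a Week 26 RHC and the reason: death, PAH worsening, AE or other.
2. For PVR only, add a supplementary median change by arm and overall. Rank as worst those with no Week 26 RHC because they died or stopped LTP001 for PAH worsening. Restrict this to PVR, because worst has no obvious direction for parameters such as heart rate or PCWP.
3. Label the existing summary as covering participants with a Week 26 RHC, and state whether values taken after stopping LTP001 are included. A label saying that they were all still on drug could be false.

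Separately, the sponsor should reconcile Protocol 1.3, 7.1 and the 10.2.2 definition on whether the Week 26 RHC is kept after treatment discontinuation.

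The cost is a few lines of SAP text, one table and one extra PVR summary. The supplementary median answers a composite question, so it must be labelled as such, and it will be slightly less favourable than the observed-case result. The existing summary stays as planned.
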